3.2 External datasets

Screening logs were received from each site on a monthly basis via the University of York DropOff Service.

Data was downloaded from the following websites to calculate the index of multiple deprivation for postcodes in England, Wales, Scotland and Northern Ireland:

- https://www.gov.uk/government/statistics/english-indices-of-deprivation-2015 (accessed 08/10/2018, published September 2015)
- https://statswales.gov.wales/Catalogue/Community-Safety-and-Social-Inclusion/Welsh-Index-of-Multiple-Deprivation/WIMD-2014/wimd2014 (accessed 08/10/2018, published November 2014)
- https://www.gov.scot/Topics/Statistics/SIMD (accessed 08/10/2018, published August 2016)
- https://ons.maps.arcgis.com/home/item.html?id=ef72efd6adf64b11a2228f7b3e95dee
 a (accessed 08/10/2018, published August 2016)

https://www.nisra.gov.uk/publications/nimdm17-sa-level-results (accessed 27/08/2018, published November 2017)

The postcodes for Northern Ireland were downloaded from the Central Postcode Directory on 27/08/2018, and were published in November 2015. Data from the Central Postcode Directory is not freely available to the public.

3.3 Management of Datasets and Data Verification

The Database Management Company has a long history of managing government related services and is able to demonstrate commitment to data security and quality management through ISO27001 and ISO9001 accreditations and recent GDPR legislation. ISO27001 accredited Information Security Management Systems demand that all of systems and processes are maintained with confidentiality, integrity and availability of data at the core. In addition, the Database Management Company is ISO9001 accredited, the internationally recognized standard for Quality Management Systems. Regular external audits ensure adherence to ISO9001 and ISO27001 standards.

The Business Requirements Specification documents stored in the Y Drive contain comprehensive details of both functional and non-functional requirements of the study database. These documents incorporate all data validation/verification rules applied.

3.4 Location of Data and Associated Files

Data and documents relevant to the statistical analysis will be kept electronically (Y:\ Project -- A - Statistics).

4 Analysis

4.1 Strategy for reporting data and general considerations

Data will be analysed and reported according to CONSORT guidelines [5]. A CONSORT diagram will be produced (see Figure 2). Analyses will be conducted using Stata version 16 or later [6]. The version of Stata to be used will be confirmed in the final report. All analyses will be conducted following the principle of intention-to-treat unless stated otherwise. Statistical tests will be two-sided at the 5% significance level. Effect size estimates will be presented with 95% confidence intervals.

4.2 Recruitment and attrition

The number of participants screened, consented and randomised to the trial will be reported, along with reasons for ineligibility. All withdrawals will be reported along with the reasons, where given, for withdrawal.

4.3 Baseline data

All baseline data will be summarised descriptively by trial arm. In addition, baseline data by trial arm will be presented for those who provided a smoking status at the primary outcome follow-up (Table 4) [7]. No formal statistical comparisons will be undertaken [8]. Continuous measures will be reported as means and standard deviations (and/or median, interquartile range, and minimum and maximum as appropriate) while categorical data will be reported as counts and percentages.

4.4 Primary outcome analysis

The primary outcome will be analysed using a mixed-effects logistic regression model adjusting for treatment group, age, years of smoking, income status (as measured by the IMD quintile within the participant's nation), level of smoking (as measured by the Fagerström score) and whether the primary outcome was collected before the 16th of March

2020 (the date on which the intervention changed due to the Covid-19 pandemic), with centre as a random effect.

For a small number of participants in Belfast, a biochemical sample was provided but due to a miscommunication with the lab the sample was not analysed for anabasine. It was decided with the TSC that in this scenario, those who self-reported as quit and had a CO reading less less than 4 ppm would be classed as non-smokers for the primary analysis.

If a participant is missing data on the primary outcome, it shall be assumed the participant is smoking, as per the Russell Standard [9]. If a participant is missing data on any covariates to be included in the analysis models, the missing values will be replaced with centre-specific means [10]. The assumptions of the model will be checked. If the assumptions are found to be questionable, the data will be transformed or non-parametric data analysis methods will be used.

It was considered whether sparse data bias would be an issue when conducting the primary analysis [11]. Given the sample size calculation assumption that 7% of participants in the control group would quit, it can be assumed that if the full sample size of 940 are recruited and the intervention has no effect, then the 'event' of a participant quitting smoking at the late pregnancy stage would be expected to occur approximately 66 times during the study. The primary analysis model contains five fixed effect variables, which means approximately 13 events per variable are expected. This exceeds the recommended minimum of 10 events per variable when using logistic regression and as a result it was not considered necessary to use an alternative statistical model [12].

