2.7 Randomisation

Participants were allocated using a 1:1 allocation ratio to either intervention or control using random permuted blocks with randomly varying block sizes. No stratification factors were used when randomising the participants.

To try to prevent participants in the incentives arm using the timing of the primary outcome to 'game' the study and falsely obtain the final incentives voucher, all participants were randomly assigned a date for primary outcome follow-up between 34 and 38 weeks gestation, which was calculated using the participant's EDD.

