2.9.4 Follow-up 4: Late pregnancy (34-38 weeks gestation)

All participants were followed up at the primary outcome stage in late pregnancy. Follow-up telephone contact was attempted by the trial contact centre at a random date between 34 and 38 weeks gestation allocated at the time of initial randomisation. Trial research nurses reviewed participants' notes one week prior to the telephone contact to check the health status of mother and baby and alert TCC staff to any adverse events e.g. miscarriage or stillbirth, that required particular sensitivity when conducting follow-up. TCC staff were blind to group allocation.

Three attempts were made by the TCC to contact women. If no contact was established, local research staff followed up women by telephone, text, and letter. On successful contact, women were asked: 'Have you smoked in the last 8 weeks?' If yes, 'Have you smoked more than 5 cigarettes in that time?'. EQ-5D-5L data, and current NRT/electronic cigarette use were also collected at this time point.

Self-report of not smoking was corroborated by cotinine estimation on saliva or urine (when saliva collection could not be tolerated). Where women were using NRT or e-cigarettes, anabasine assay on saliva was also conducted. Cotinine and anabasine were assayed by ABS Laboratories Limited (https://www.acmgloballab.com/about-us/our-locations/europe-london-uk). To minimise the potential for women to 'game' the primary outcome, incentive payments were dependent on the CO result, which is an immediate measure, and not on the cotinine or anabasine level.

An important aspect of the primary outcome for this phase III trial is the proportion of women successfully followed up in both the intervention and control group. To minimise loss to follow-up, particularly among controls, women in both groups will receive Love2Shop vouchers of £50 and £25 for providing data and saliva/urine samples where applicable at the primary (late pregnancy) and secondary (six months post-partum) outcome time points respectively (Figure 2.).

To assess if a) women lost to trial follow-up are still smoking towards the end of pregnancy, and b) the primary outcome has been 'gamed' (saliva cotinine below the cut-off but still smoking in late pregnancy) residual blood from routine late pregnancy samples, where available, will be tested.

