4.5 Secondary outcome analyses

Engagement with SSS will be analysed using a mixed-effects logistic regression model adjusting for treatment group, age, years of smoking, income status, level of smoking (as measured by the Fagerström score) and whether the engagement data was collected before the 16th of March 2020, with centre as a random effect.

CO-validated smoking status at 4 weeks post-quit date will be analysed using a mixedeffects logistic regression model, adjusting for treatment group, age, years of smoking, income status, level of smoking (as measured by the Fagerström score) and whether the CO-validated smoking status was collected before the 16th of March 2020, with centre as a random effect. If a participant is missing their smoking status, it shall be assumed the participant is smoking.

Birth weight will be analysed using a mixed-effects linear regression model, adjusting for treatment group, the age, height and weight of the mother at booking, years of smoking, income status, level of smoking (as measured by the Fagerström score) and whether the birthweight data was collected before the 16th of March 2020 as fixed effects, and centre as a random effect. If a participant is missing data on birth weight, it shall be assumed the data is missing at random conditional on the covariates included in the analysis model [13, 14].

Continuous and point abstinence outcomes obtained at six months postpartum will be analysed using mixed-effects logistic regression adjusting for the same covariates and applying the same assumptions used in the primary outcome analysis (with the exception that whether the postpartum point abstinence outcome was collected before 16th of March 2020 will be adjusted for instead of adjusting for whether the primary outcome was collected before the 16th of March 2020). If a participant is missing their smoking status, it shall be assumed the participant is smoking. Participants who at postpartum were followed up earlier than 6 months will be excluded from the analysis of continuous and point abstinence

outcomes obtained at six months postpartum, and will be accounted for in a sensitivity analysis.

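### The pre/post-16 March 2020 covariate is defined by actual collection, so women counted as smokers with nothing collected have no clear value; define it from dates fixed at randomisation

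*SAP*

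**What the plan says.** Section 4.4 fits a mixed-effects logistic model with treatment, age, years of smoking, IMD quintile, Fagerström score and "whether the primary outcome was collected before the 16th of March" 2020, described as "the date on which the intervention changed due to the Covid-19 pandemic". Two rules in the same section bear on women who were not followed up:

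- Outcome: "If a participant is missing data on the primary outcome, it shall be assumed the participant is smoking, as per the Russell Standard".
- Covariates: "If a participant is missing data on any covariates to be included in the analysis models, the missing values will be replaced with centre-specific means".

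Nothing states which period a woman belongs to when no outcome was obtained from her.

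A scheduled date does exist for everyone. Section 2.7 says "all participants were randomly assigned a date for primary outcome follow-up between 34 and 38 weeks gestation", and section 2.9.4 says contact was attempted "at a random date between 34 and 38 weeks gestation allocated at the time of initial randomisation".

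Section 4.5 gives each secondary outcome its own version of the indicator. Section 4.7.1 (Firth model) reuses the primary one, and section 4.7.2 plans a treatment-by-period interaction if descriptive checks suggest a Covid effect. For the four-week outcome, section 2.9.2 seeks status only for women who engaged and set a quit date, and section 2.5.2.2 says no CO sample was possible when that follow-up fell due after 16 March 2020.

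**The concern.** The covariate is meant to capture calendar period, which arm cannot affect. Defined by actual collection, it also depends on whether, and how quickly, a woman was reached. Section 2.9.4 expects retention to be harder among controls, so response may well differ by arm.

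Asked whether the outcome was collected before 16 March, one can answer 'no' for a woman never reached. On that reading no covariate is missing and the centre-mean rule never applies. The 'no' group then combines true post-Covid women with every non-responder, all coded as smokers. On the other reading the value is missing and a centre mean is inserted. The two readings can give different primary odds ratios. Section 2.8 says the statistician is not blinded, so the choice should not be left to the analysis stage.

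**Working it through.** **Inputs from the SAP.** Quit rates 7% v 14%, 90% power, two-sided 5%, 15% loss, 470 per arm (sections 2.6 and 4.1).

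**Plan's own figure.** n per arm = [1.96√(2p̄(1−p̄)) + 1.282√(p₁(1−p₁)+p₂(1−p₂))]² / (p₂−p₁)², with p₁ = 0.07, p₂ = 0.14 and p̄ = 0.105, gives 401. Then 401/0.85 = 472 per arm, or 944 in all, against 940 stated. The sample size reproduces, and this point does not depend on it. The reference odds ratio is (0.14/0.86)/(0.07/0.93) = 2.163.

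**Assumptions not in the SAP.** Share of scheduled dates before 16 March; loss by arm; no true Covid effect unless stated; scheduled date unrelated to response. The outcome with missing counted as smoking is regressed on arm and period in a large-sample logistic fit. Centre and the other covariates are left out.

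**Mechanism under the literal reading** (true null at 7% in both arms, 80% of dates before, loss 30% control v 15% incentives):

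- Control: 'yes' cell 0.80 × 0.70 = 0.56 of women, quit rate 0.07/0.70 = 10.0%. 'No' cell 0.44, quit rate (0.20 × 0.07)/0.44 = 3.2%.
- Incentives: 'yes' cell 0.80 × 0.85 = 0.68, quit rate 0.07/0.85 = 8.2%. 'No' cell 0.32, quit rate 0.014/0.32 = 4.4%.

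The within-cell odds ratios are about 0.81 ('yes') and 1.39 ('no'), although the truth is 1.00 in both. The adjusted common odds ratio is 0.90.

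**Treatment odds ratio under the literal reading:**

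| Loss, control v incentives | Dates before 16 March | 2.16 becomes | 1.00 becomes |
|---|---|---|---|
| 30% v 15% | 80% | 1.98 | 0.90 |
| 30% v 15% | 90% | 1.91 | 0.87 |
| 20% v 10% | 80% | 2.08 | 0.95 |
| 20% v 10% | 90% | 2.03 | 0.93 |

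Over a wider grid the literal reading gives 1.875 to 2.438 (null 0.854 to 1.104). That grid has 50% to 90% of dates before; loss of 15/15, 20/10, 10/20 or 25/10%; a Covid odds ratio of 1 or 0.5; and 0 or 10 points more loss after the date. The shift favours the intervention when the incentives arm loses more.

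**Centre-mean reading, same grid:** 2.151 to 2.167 (null 0.995 to 1.003), at most about 0.6% from the scheduled-date model.

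**Spurious Covid effect.** With 30% v 15% loss the literal reading shows a Covid odds ratio of about 2.5 (80% before) to 4 (90% before) when none exists. Equal loss does not remove it. With 15% in each arm, a 7% null and 80% before, 'yes' has quit rate 0.07/0.85 = 8.24% (odds 0.0897) and 'no' has 0.014/0.32 = 4.375% (odds 0.0457), a ratio of 1.96.

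**Interaction model.** With 80% before and 20% v 10% loss, a constant 2.16 splits under the literal reading into 1.92 pre and 2.75 post. A true null splits into 0.88 and 1.30.

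**Four-week model.** Assume 40% v 60% engage and 20% of engagers quit in both arms. The pre-Covid intention-to-treat rates are 0.40 × 0.20 = 8% and 0.60 × 0.20 = 12%, so the odds ratio is (0.12/0.88)/(0.08/0.92) = 1.57. Under the literal reading every validated quitter sits in the 'yes' cell, which holds only engaged pre-Covid women, at 20% in each arm. The 'no' cell has no quitters and adds no information, so the estimate is 1.00. Centre-mean filling also gives 1.00 if post-Covid women are coded 'no'.

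**The case against.** The strongest answer is that section 4.4 already has a rule for missing covariates, "the missing values will be replaced with centre-specific means", and under it the primary odds ratio is essentially unchanged. A reader might infer that adjusting for this covariate necessarily biases the primary treatment effect. The SAP does not support that. Material distortion needs both the literal coding and unequal loss; with equal loss a true null stays at 1.00 under either reading. Section 2.6 plans for 15% loss and gives no difference by arm, so 30% v 15% is a hard case.

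Also fair: smoking status is first asked by telephone, so a self-reported quitter who gives no sample still has a contact date. This reduces the number of undated women, but the SAP does not say whether the call or the sample counts as collection. Delay across the cut-off concerns only women scheduled near 16 March and was not modelled.

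A reader might extend the point to engagement, where the model adjusts for "whether the engagement data was collected before the 16th of March 2020", and argue that women who never engage have no date. Section 2.9.1 has staff ascertain and record engagement for both arms, so a 'yes' does not imply the event. For birth weight, missing outcomes are treated as missing at random and not counted as events, so this mechanism is absent.

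What remains is that the rule's scope is uncertain for this variable. A fraction is a poor value for a yes/no period and cannot place a woman before or after the date in the section 4.7.2 interaction model. The rule does not protect the four-week model.

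**Conclusion.** The point holds as a conditional weakness of moderate severity. The primary indicator rests on a post-randomisation event and has no natural value for women kept in as smokers with nothing collected. The SAP's centre-mean rule leaves the primary odds ratio within about 0.6%. The literal reading, equally open on the text, takes 2.16 to about 1.9 to 2.0 with 30% v 15% loss and to about 2.03 to 2.08 with 20% v 10%, in each case with 80% to 90% of dates before 16 March. It also shows a Covid effect that is not there, even with equal loss. The four-week model is the most exposed: in the illustration the effect disappears (1.57 to 1.00). Loss, calendar split and engagement rates are assumptions, so these figures show sensitivity and do not forecast the trial's result.

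**What to change.** Define the pre/post-16 March 2020 indicator for every randomised woman from dates that depend on neither arm nor response:

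- Primary outcome (section 4.4, the Firth model in 4.7.1 and the interaction model in 4.7.2): the late-pregnancy contact date allocated at randomisation.
- Point and continuous postpartum abstinence (4.5): EDD plus six months.
- Four-week outcome (4.5): a date available for all women, such as the randomisation date plus one fixed interval used in both arms, and not the quit date or the collection date.

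State that this indicator is never filled with centre means. The descriptive Covid tables in 4.7.2 may keep actual collection timing, which is informative there. Engagement and birth weight need no change on this ground.

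The cost is a few lines of SAP wording and one derived variable per outcome. The EDD and allocated contact date are already held, as the randomisation date should be, so no new data are needed.

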2.6 Sample size

The aim was to recruit 940 participants to the trial (470 per arm). This gave 90% power to detect a doubling of the smoking cessation rate from 7% to 14%, allowing 15% loss to follow-up. The smoking cessation rate in the control group was derived from the smoking cessation rate found in the feasibility trial [2], and two other large trials of smoking cessation interventions in pregnant smokers [3, 4]. The smoking cessation rate in the intervention group was derived from the cessation rate in the feasibility trial, along with considerations of the effect size that would be considered clinically important.

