4.7 Sensitivity analyses

4.7.1 Sensitivity of primary analysis to sparse data bias

To assess the sensitivity of the primary analysis to sparse data bias, the primary outcome will be analysed using a Firth logistic regression model adjusting for treatment group, age, years of smoking, income status (as measured by IMD score), level of smoking (as measured by the Fagerström score), whether the primary outcome was collected before the 16th of March 2020 and site [11]. All variables will be adjusted for as fixed effects, as the Stata command used to implement Firth logistic regression cannot incorporate random effects.

4.7.2 Impact of the Covid-19 pandemic on analysis of the primary and secondary smoking outcomes

To assess the impact of the Covid-19 pandemic on the primary and secondary smoking outcomes, the number of self-reported non-smokers pre-Covid and post-Covid will be compared descriptively by treatment group (Table 6). This will allow assessment of the possibility that participants in the incentives group were more likely to report as non-smokers to receive financial incentives post-Covid compared to pre-Covid. In addition, the number of participants who self-reported as non-smokers but provided a positive biochemical sample pre-Covid and post-Covid will be compared descriptively by treatment group (Table 7).

The number of biochemically verified non-smokers pre-Covid and post-Covid will also be compared descriptively by treatment group (Table 8), in order to assess the possibility that the treatment effect pre-Covid is different to the treatment effect post-Covid.

If the above checks indicate the Covid-19 pandemic had an impact on the analysis of the primary and secondary smoking outcomes, the analyses of these outcomes shall be repeated with the addition of an interaction term between treatment allocation and a pre-Covid/post-Covid variable, with effect size estimates pre-Covid and post-Covid presented alongside corresponding 95% confidence intervals and p-values.

Finally, in order to assess whether the change in intervention had an impact on the return of biochemical samples, the number of returned biochemical samples pre-Covid and post-Covid will be compared descriptively by treatment group in the subset of self-reported non-smokers (Table 9).

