4.7.3 Subgroup analyses

The primary analysis will be repeated, with the addition of interaction terms between treatment group and each of the following covariates:

- Maternal age (≤28 years vs >28 years, with 28 years being the mean age of a first time mother according to the ONS in 2015)
- Index of multiple deprivation quintile (1/2/3/4/5)
- Years of smoking (≤10 years vs >10 years)
- Fagerström score (the cut-off will be decided using data on the distribution of the Fagerström score in the previous CPIT RCT)

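### The sparse-data check for the primary model counts five fixed effects where SAP 4.4 lists six, so about 11 events per variable are expected, not 13; the form of the IMD covariate also needs fixing

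*SAP*

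**What the plan says.** SAP 4.4 fits a mixed-effects logistic regression to the primary outcome. Its fixed effects are treatment group, age, years of smoking, IMD quintile within the participant's nation, Fagerström score, and an indicator for whether the outcome was collected before 16 March 2020. Centre is a random effect.

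The section then asks whether sparse-data bias is a risk. It starts from the design rate ("Given the sample size calculation assumption that 7% of participants in the control group would quit") and takes the case "if the full sample size of 940 are recruited and the intervention has no effect", which gives about 66 quitters. It continues: "The primary analysis model contains five fixed effect variables, which means approximately 13 events per variable are expected". It concludes: "This exceeds the recommended minimum of 10 events per variable when using logistic regression", and so sees no need for an alternative model.

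SAP 4.7.1 nevertheless plans a Firth logistic regression as a sensitivity analysis for sparse-data bias. There site becomes a fixed effect, because the Stata command cannot take random effects, and the deprivation covariate is given as "income status (as measured by IMD score".

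**The concern.** The list of model terms and the count of those terms stand in the same section and disagree. The count is the plan's written reason for keeping the standard model, so it should be right.

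The deprivation covariate raises two further questions:

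- **Coding.** A five-level quintile can enter as one numeric term or as four indicators, and the SAP does not say which. The choice decides whether the rule of 10 is met when counted per coefficient. Leaving it open also leaves an analyst's choice in the primary model.
- **Form in the Firth check.** SAP 4.4 uses a quintile within nation; 4.7.1 names a score. SAP 3.2 lists separate deprivation sources for England, Wales, Scotland and Northern Ireland, published between 2014 and 2017. The sites in Table 1 include Lanarkshire, Belfast and several in England. A quintile within nation deals with this; a raw score has no stated common scale. A check meant to isolate the effect of the estimator would then also change a covariate, for no stated reason.

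**Working it through.** **Inputs**

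- Sample size: 940, or 470 per arm (SAP 2.6 and 4.4).
- Quit rate with no intervention effect: 7% in both arms (SAP 4.4).
- Design alternative: 7% versus 14% (SAP 2.6: "This gave 90% power to detect a doubling of the smoking cessation rate from 7% to 14%, allowing 15% loss to follow-up").
- Threshold: 10 events per variable (SAP 4.4).

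**The plan's own figure**

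Expected events = 940 × 0.07 = 65.8, stated as about 66.
Events per variable = 65.8 / 5 = 13.2, stated as about 13.

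The arithmetic reproduces; the divisor is what is wrong.

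**Count of fixed effects from the model statement in 4.4**

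1. Treatment group
2. Age
3. Years of smoking
4. IMD quintile
5. Fagerström score
6. Collected before 16 March 2020

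Centre is random and is not counted. The total is six.

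65.8 / 6 = 10.97, or about 11.0.

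**Count of coefficients if IMD quintile is categorical**

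Five single-coefficient terms plus 5 − 1 = 4 IMD indicators = 9.

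65.8 / 9 = 7.31, or about 7.3.

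Since 65.8 / 10 = 6.58, the no-effect case supports at most six coefficients at 10 events each. Six single-coefficient terms use all of that.

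**The same under the design alternative**

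Expected events = 470 × 0.07 + 470 × 0.14 = 32.9 + 65.8 = 98.7.

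| Divisor | No effect (65.8 events) | 7% versus 14% (98.7 events) |
|---|---|---|
| 5 (as stated) | 13.2 | 19.7 |
| 6 (variables listed) | 11.0 | 16.5 (98.7/6 = 16.45) |
| 9 (coefficients, IMD categorical) | 7.3 | 11.0 |

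**What the SAP indicates about IMD coding**

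- Towards categories: Table 4 reports five quintile rows, and the subgroup list in 4.7.3 writes out all five levels.
- Towards a numeric term: 4.4 replaces missing covariate values with centre-specific means, which suits a numeric variable, and 4.7.1 refers to a score.
- Not decisive: Table 4 is descriptive, and 4.7.3 recodes other covariates too (age and years of smoking are split in two there). Neither settles the coding in 4.4.

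**The case against.** The strongest reply is that the plan's conclusion survives the only firm error. Its criterion is worded per variable, six variables give 11.0, and 11.0 is above 10. This stands.

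A reader might go further and infer that the true figure is 7.3 and that the justification for the primary model fails. The documents do not support that. The 7.3 needs a categorical coding that the SAP does not fix and a per-coefficient count that it does not state. It also uses the no-effect scenario, which gives fewer events than the design alternative. If the trial performs as designed, even nine coefficients have about 11.0 events each. The planned Firth analysis covers the remaining risk whatever the ratio is.

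Leaving treatment out of the count would give five, but that does not rescue the text, which refers to the fixed effect variables in the model, and treatment is one of them. A reader might instead infer that the count was not revised when the March 2020 indicator came in. The amendment log records that covariate being added to other analyses and does not mention the primary model, so the cause cannot be established, and the error does not depend on it.

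On the IMD wording, it can fairly be said that SAP 2.5.4 derives only a ranking and a quintile, so the score in 4.7.1 may simply be loose wording for the quintile. That is possible, and it is a reason to align the text. A reader might also infer that aligning it would make the two models differ in estimator alone. It would not: the Firth model also treats site as fixed, as the SAP openly says. Aligning IMD removes an unnecessary difference, not the only one.

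**Conclusion.** The count in SAP 4.4 is wrong. Six fixed effects are listed and five are counted, so the stated 13 events per variable should be about 11.0. The stated criterion is still met, with a margin of 65.8 − 60 = 5.8 expected events instead of 65.8 − 50 = 15.8. This rests on the plan's own inputs: full recruitment of 940, 7% quitting in both arms, and centre left out of the count.

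The figure of 7.3 is conditional on categorical IMD coding, counting per coefficient, and no intervention effect. Under those three conditions the rule of 10 would not hold; under the design alternative it would (11.0).

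The difference between the IMD score in 4.7.1 and the within-nation quintile in 4.4 is a separate inconsistency. Its practical effect cannot be sized from the document.

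None of this shows that the primary model is unsuitable or that its estimate will be biased. The point is a correction to a stated justification, together with a covariate that should be specified once and used consistently.

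**What to change.** 1. In SAP 4.4, change the number of fixed effect variables from five to six and the ratio from 13 to about 11.
2. In 4.4, state whether IMD quintile enters as categories or as a single numeric term. Choose on how deprivation is expected to relate to quitting, not to clear the threshold.
3. If it is categorical, report about 7.3 events per coefficient in the no-effect case, and rest the justification on the planned Firth analysis instead of the rule of 10.
4. In 4.7.1, replace the IMD score with the within-nation IMD quintile, in the same coding as 4.4.
5. Record the changes in the SAP amendment log.

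The cost is wording only, with no new data, recruitment or analysis. The downside is a stated ratio that looks slightly less favourable.

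### Section 4.4 counts five fixed effects where it lists six, so the expected events per variable are about 11, not 13; the SAP's minimum of 10 is still met, but only by about one.

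*SAP*

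**What the plan says.** SAP section 4.4 specifies a mixed-effects logistic regression "adjusting for treatment group, age, years of smoking, income status (as measured by the IMD quintile within the participant's nation), level of smoking" (the Fagerström score), plus "whether the primary outcome was collected before the 16th of March" 2020, "with centre as a random effect". That makes six fixed effects and one random effect.

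Later in the section the SAP considers sparse data bias. It starts from the planning rate ("Given the sample size calculation assumption that 7% of participants in the control group would quit"), supposes that all 940 women are recruited and that the intervention has no effect, and concludes that quitting is "expected to occur approximately 66 times during the study". It continues: "The primary analysis model contains five fixed effect variables, which means approximately 13 events per variable are expected". Then: "This exceeds the recommended minimum of 10 events per variable when using logistic regression". On that basis it decides that no alternative model is needed.

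Section 4.7.1 nevertheless plans a Firth logistic regression as a sensitivity analysis for sparse data bias. It uses the same six terms plus site, all as fixed effects, and describes IMD there as a score.

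**The concern.** The number of fixed effects contradicts the list in the same section, and the figure of 13 depends on that number. The SAP compares the figure with a threshold and draws a modelling decision from it, so the miscount makes the margin look more comfortable than it is.

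Two further points bear on how thin the margin is:

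- **IMD coding.** The SAP does not say whether IMD quintile enters the primary model as one numeric term or as categories. Categories would cost four parameters instead of one.
- **Loss to follow-up.** The 66 events apply 7% to all 940 women. Section 2.6 allows for 15% loss, and section 4.4 classes women with a missing outcome as smokers, so lost women add no events.

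At stake is whether the stated justification for an ordinary mixed logistic model is right as written. The validity of the primary analysis itself is not in question.

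**Working it through.** **Inputs (all from the SAP)**

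- N = 940 and quit rate p = 7%, applied to both arms in the no-effect case (sections 2.6 and 4.4).
- Number of fixed effects: k = 5 as stated, k = 6 as listed (section 4.4).
- Minimum adopted: 10 events per variable (section 4.4).
- IMD quintile: five levels, shown as categories in Table 4 and in the subgroup list ("Index of multiple deprivation quintile (1/2/3/4/5") of section 4.7.3.
- Loss to follow-up: 15% (section 2.6).

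**Formula:** events per variable = N × p / k.

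**1. The SAP's own figure.** 940 × 0.07 = 65.8, about 66 events. 65.8 / 5 = 13.2. This reproduces the stated 13, and only k = 5 gives it.

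**2. The count as listed.** Treatment group (1), age (2), years of smoking (3), IMD quintile (4), Fagerström score (5), 16 March 2020 indicator (6). 65.8 / 6 = 10.97, about 11. The margin over 10 is 0.97, against 3.2 as stated.

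**3. If IMD enters as categories (coding not stated).** Five single-parameter terms plus four dummy terms make nine parameters. 65.8 / 9 = 7.3 per parameter.

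**4. If the 7% applies only to women followed up (assumption).** 940 × 0.85 = 799 women; 799 × 0.07 = 55.9, about 56 events. Per variable: 55.9 / 6 = 9.3. Per parameter with categorical IMD: 55.9 / 9 = 6.2.

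**5. Under the design alternative of 7% against 14%.** 470 × 0.07 + 470 × 0.14 = 98.7 events. Per variable: 98.7 / 6 = 16.5. Per parameter with categorical IMD: 98.7 / 9 = 11.0.

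| Scenario | Events | Six variables | Nine parameters |
|---|---|---|---|
| No effect, all 940 (the SAP's basis) | 65.8 | 11.0 | 7.3 |
| No effect, 7% of the 85% followed up | 55.9 | 9.3 | 6.2 |
| 7% against 14%, all 940 | 98.7 | 16.5 | 11.0 |

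**The case against.** The strongest reply is that nothing turns on the miscount. The SAP's rule is worded per variable, six variables give 11, and 11 exceeds 10, so the SAP's conclusion still follows. The no-effect case is also the low-event case; if the intervention works as designed, there are 16.5 events per variable. This stands.

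A reader might go further and infer that the plan fails its own minimum. The documents do not support that:

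- **The figure of 7.3** needs a per-parameter rule in place of the per-variable one, and a categorical coding that the SAP never gives for the primary model. Table 4 is descriptive. The subgroup list in section 4.7.3 also splits age and years of smoking into two groups, so it does not fix how covariates enter the main model. Filling missing covariates with centre-specific means (section 4.4) and the reference to an IMD score (section 4.7.1) point, if anything, to a numeric term.
- **The figure of 9.3** rests on applying 7% to women followed up only. The sample size arithmetic is compatible with that: a standard two-proportion calculation gives 401 per arm, and 401 / 0.85 = 472, close to the stated 470. But the SAP does not say so, and the earlier trials behind the 7% may already have counted lost women as smokers.

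A reader might also infer that the primary estimate would be biased. A simulation of the nine-parameter, no-effect case (about 1,500 trials, ordinary logistic regression, no centre effect, covariates unrelated to outcome) gave an average treatment odds ratio of 0.995 with 95.9% coverage at about 66 events, and 0.990 with 95.3% at about 56. It is simplified, but gives no sign of harm. The Firth check is in any case already planned.

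One defence does not work. Reading the five as the covariates other than treatment fails, because treatment group is itself an estimated fixed effect.

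**Conclusion.** The point holds as a minor correction. Section 4.4 contradicts itself on the number of fixed effects, and no other part of the SAP puts it right. The figure should be about 11 events per variable, not 13, on the SAP's own assumptions of 940 women, 7% quitting and no intervention effect. The stated minimum is still met, with a margin of about one and not three.

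The values below 10 are conditional. About 7 per parameter requires categorical IMD and a per-parameter count; about 9 per variable requires the 7% to apply only to those followed up. They show how thin the margin is, not that the rule is broken.

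It is tempting to suppose that the count was not updated when the 16 March 2020 indicator was added. The amendment log does not mention that change for the primary model, and the point does not depend on it.

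**What to change.** In section 4.4:

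1. Restate the count as six fixed effect variables and the figure as approximately 11 events per variable.
2. State whether IMD quintile enters the primary model as a numeric term or as categories. If categories, give the per-parameter figure (about 7 on 66 events) and say how a missing quintile is filled, since a centre mean need not be one of the five categories. Keep the wording consistent with the IMD score named in section 4.7.1.
3. Cite the Firth analysis in section 4.7.1 as the safeguard, given the thin margin, in place of relying on the events-per-variable figure alone.

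Stating the intended coding is enough; this point gives no reason to prescribe one, and the primary model stays as it is. The cost is a few words and a slightly less favourable stated figure.
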